### 6.2.5 Child-Turcotte-Pugh Score

The Child-Turcotte-Pugh score provides an assessment of the prognosis of chronic liver disease. In this classification system, various laboratory and clinical parameters are scored as shown in [Table 6-1](#).

**Table 6-1 Child-Turcotte-Pugh Scoring System**

Categories	Scoring System
Bilirubin	+1: <2 mg/dL +2: 2-3 mg/dL +3: >3 mg/dL
Albumin	+1: >3.5 g/dL +2: 2.8-3.5 g/dL +3: <2.8 g/dL
International normalized ratio	+1: <1.7 +2: 1.7-2.2 +3: >2.2
Ascites	+1: No ascites +2: Ascites, medically controlled +3: Ascites, poorly controlled
Encephalopathy	+1: No encephalopathy +2: Encephalopathy, medically controlled +3: Encephalopathy, poorly controlled

The total score determines the classification as show in [Table 6-2](#).

**Table 6-2 Child-Turcotte-Pugh Classification**

Points	Class	One-Year Survival	Two-Year Survival
5-6	A	100%	85%
7-9	B	81%	57%
10-15	C	45%	35%

The subjects enrolled in this study will have Class A, well-compensated cirrhosis with a nearly 100% one-year survival. Additionally, a 2-point increase in the actual score will be used as an indication of progression of disease.

### **6.2.6 MELD Score**

The MELD score assesses the severity of chronic liver disease and is used for prioritizing allocation of liver transplants. The MELD score will be calculated from laboratory tests (serum bilirubin, serum creatinine, and prothrombin time INR).

MELD score =  $(0.957 \times \ln(\text{serum creatinine}) + 0.378 \times \ln(\text{serum bilirubin}) + 1.120 \times \ln(\text{INR}) + 0.643) \times 10$  (if hemodialysis, value for creatinine is automatically set to 4.0)

Note: If any score is less than 1, the MELD assumes the score is equal to 1.

### **6.2.7 EGD Evaluation**

Subjects will undergo an EGD within 2 months prior to randomization and within 14 to 28 days after the final 26th dose of IMP or where feasible following study termination and the following information will be collected.

Esophageal varices, if present, will be classified as follows:

1. Large varices >50% impingement on the lumen;
2. Small varices <25% impingement on lumen;
3. Medium varices are intermediate between small and large varices.

Subjects with medium or large varices or varices with red signs, regardless of size, will be excluded from study participation. Red signs include red wale markings (dilated venules oriented longitudinally on the variceal surface), cherry red spots (small, red, spotty dilated venules usually about 2 mm in diameter on the variceal surface) or hematocystic spots (large, round, crimson red projection greater than 3 mm that looks like a blood blister on the variceal surface). Subjects without varices or with small varices will advance to HVPG measurement and liver biopsy. Consistent with the American Association for the Study of Liver Disease practice guidelines ([Garcia-Tsao 2007](#)), subjects with small varices will not receive treatment

with nonselective  $\beta$ -adrenergic inhibitors or variceal ligation therapy during the clinical study since long-term benefit has not been established for small varices. At the discretion of the principal investigator, subjects who have no varices or small varices and are currently on  $\beta$ -adrenergic inhibitors may be withdrawn from therapy at least 4 weeks prior to randomization.

## **6.3 Exploratory Assessments**

### **6.3.1 Chronic Liver Disease Questionnaire**

The CLDQ is a tool used to measure health-related quality of life in subjects with liver disease and has demonstrated good reliability and validity in subjects with chronic liver disease (Younossi 1999). The instrument includes 29 questions with 6 domains: abdominal symptoms, systemic symptoms, fatigue, activity, emotional function, and worry. The CLDQ will be given to the subject at the beginning of the visit (Table 12-2), and will be considered source documentation. The CLDQ is provided in Section 12.3.

### **6.3.2 Biomarkers**

Blood will be collected for assessment of biomarkers (Table 12-2). Tests will include the ELF test, FibroTest (FibroSure), and galectin-3. At each of these times, a blood sample will be frozen ( $-20^{\circ}\text{C}$ ;  $-4^{\circ}\text{F}$ ) and held before treatment and at the end of treatment for other possible poststudy biomarker testing.

#### **6.3.2.1 Enhanced Liver Fibrosis Test**

The ELF is a method to predict the severity and clinical outcome in chronic liver diseases. The ELF test uses a routine blood sample to measure procollagen-III aminoterminal-propeptide, tissue inhibitor of matrix metalloproteinase-1, and hyaluronic acid.

#### **6.3.2.2 FibroTest/FibroSure**

The FibroTest score (FibroSure in the United States), is a composite score that has been correlated with the extent of liver fibrosis. This score is calculated from the subject's age,

sex, alpha-2-macroglobulin, haptoglobin, apolipoprotein A1,  $\gamma$ -glutamyl transpeptidase, and total bilirubin.

### **6.3.2.3 Galectin-3**

Blood will be collected for assessment of galectin-3 ([Table 12-2](#)).

### **6.3.3 Plasma and Serum Samples**

Plasma and serum samples will be collected at Visits 1, 13, and 26 ([Table 12-2](#)). These samples will be stored at at  $-20^{\circ}\text{C}$ .

## **6.4 Safety Assessments**

All subjects receiving any part of at least 1 infusion of study treatment will be evaluated for safety. Safety assessments will include incidence of AEs during study treatment, emergent physical examination abnormalities, emergent vital sign and ECG abnormalities, and laboratory parameter abnormalities.

### **6.4.1 Vital Sign Measurements**

Vital sign measurements (including heart and respiratory rate, blood pressure, and body temperature) will be collected before administration of IMP ([Table 12-1](#) and [Table 12-2](#)).

Blood pressure will be obtained with the subject in the supine position and measured twice consecutively with a 1-minute interval between measurements. The average of the 2 measurements will be recorded.

### **6.4.2 Physical Examination**

A complete physical examination, including height and weight, will be performed at screening, with particular attention to examination for stigmata of liver disease/cirrhosis ([Table 12-1](#)). A limited physical examination will only include weight and examination of the heart, lung, and abdomen during the treatment phase ([Table 12-2](#)).

### **6.4.3 Electrocardiogram**

A standard 12-lead ECG will be performed during screening and the treatment phase ([Table 12-1](#) and [Table 12-2](#)).

Twelve-lead ECGs will be systematically digitally recorded after the subject has been in the supine position for at least 10 minutes. The electrodes will be positioned in the same location on the subject for each ECG recording. Electrocardiograms will be recorded before blood sampling.

### **6.4.4 Chest Radiograph**

Chest radiographs (posterior-anterior and lateral views) will be performed at screening ([Table 12-1](#)).

### **6.4.5 Adverse Events**

#### **6.4.5.1 Definitions of Adverse Events**

The investigator is responsible for reporting all treatment-emergent AEs (TEAEs) that are observed or reported during the study, regardless of their relationship to IMP or their clinical significance.

An AE is defined as any untoward medical occurrence in a subject enrolled into this study, regardless of its causal relationship to IMP. Subjects will be instructed to contact the investigator at any time after randomization if any symptoms develop.

A TEAE is defined as any event not present before exposure to IMP or any event already present that worsens in either intensity or frequency after exposure to IMP.

An SAE is defined as any event that results in death, is immediately life threatening, requires inpatient hospitalization or prolongation of existing hospitalization, results in persistent or significant disability/incapacity, or is a congenital anomaly/birth defect. Important medical events that may not result in death, be life threatening, or require hospitalization may be considered SAEs when, based upon appropriate medical judgment, they may jeopardize the subject or may require medical or surgical intervention to prevent one of the outcomes listed in this definition. Examples of such medical events include allergic bronchospasm requiring

intensive treatment in an emergency room or at home, blood dyscrasias or convulsions that do not result in inpatient hospitalization, or the development of drug dependency or drug abuse.

#### **6.4.5.2 Eliciting and Documenting Adverse Events**

All AEs (serious and nonserious) will be assessed beginning at screening and up to 42 days after the last dose of IMP.

Serious AEs that occur more than 42 days after the last dose of IMP need not be reported unless the investigator considers them related to IMP.

At every study visit, subjects will be asked a standard nonleading question to elicit any medically related changes in their well-being. They will also be asked if they have been hospitalized, had any accidents, used any new medications, or changed concomitant medication regimens (both prescription and over-the-counter medications).

In addition to subject observations, AEs identified from any study data (eg, laboratory values, physical examination findings, ECG changes) or identified from review of other documents that are relevant to subject safety will be documented on the AE page in the eCRF.

#### **6.4.5.3 Reporting Adverse Events**

All AEs reported or observed during the study will be recorded on the AE page in the eCRF. Information to be collected includes drug treatment, dose, event term, time of onset, investigator-specified assessment of severity and relationship to IMP, time of resolution of the event, seriousness, any required treatment or evaluations, and outcome. Adverse events resulting from concurrent illnesses, reactions to concurrent illnesses, reactions to concurrent medications, or progression of disease states must also be reported. All AEs will be followed to adequate resolution. The Medical Dictionary for Regulatory Activities (MedDRA, Version 17.1) will be used to code all AEs.

Any medical condition that is present at the time that the subject is screened but does not deteriorate should not be reported as an AE. However, if the subject's condition deteriorates at any time during the study, it should be recorded as an AE.

Any AE that meets SAE criteria ([Section 6.4.5.1](#)) must be reported to the sponsor (designee) immediately (ie, within 24 hours) after the time study center personnel first learn about the event.

Study center personnel should complete the AE eCRF using electronic data capture, designating the event as serious. If electronic data capture is unavailable, complete an SAE form using the following contact information:

**Pharmacovigilance**

**[name]**

**[name]**

**SAE [contact]**

**SAE Fax line: [name]**

#### **6.4.5.4 Assessment of Severity**

The severity, or intensity, of an AE refers to the extent to which an AE affects the subject's daily activities. The intensity of the AE will be rated as mild, moderate, or severe using the following criteria:

- Mild: These events require minimal or no treatment and do not interfere with the subject's daily activities.
- Moderate: These events result in a low level of inconvenience or concern with the therapeutic measures. Moderate events may cause some interference with normal functioning.
- Severe: These events interrupt a subject's usual daily activity and may require systemic drug therapy or other treatment. Severe events are usually incapacitating.

Changes in the severity of an AE should be documented to allow an assessment of the duration of the event at each level of intensity to be performed. Adverse events characterized as intermittent do not require documentation of onset and duration of each episode.

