**Safety Assessments:**

Safety assessments will include incidence of adverse events (AEs) during study treatment, emergent physical examination abnormalities, emergent vital sign measurements and electrocardiogram abnormalities, and laboratory parameter abnormalities.

A data safety monitoring board (DSMB) will be established that includes a panel of at least 3 independent medical experts and an unblinded biostatistician. An official charter will be established. The primary role of the DSMB will be to periodically monitor the safety of the clinical study. The DSMB will meet at several predetermined times during the study and at any other times when it is determined by the study monitors or principal investigators that such a review is warranted. An unblinded monitoring team will also be added to the study.

All subjects receiving any part of at least 1 infusion of study treatment will be evaluated for safety. The safety analyses will include evaluation of the incidence of treatment-emergent AEs (TEAEs), grade 3 or greater AEs, serious AEs (SAEs), and TEAEs leading to discontinuation of study treatment using the Common Terminology Criteria for Adverse Events Version 4.0 or higher.

**Study Drug, Dosage,  
and Route of  
Administration:**

Subjects in the GR-MD-02 treatment groups will be randomly assigned to receive either 2 mg/kg lean body weight (up to a maximum of 200 mg total) or 8 mg/kg lean body weight (up to a maximum of 800 mg total). The IMP will be diluted in 100 mL of normal saline and infused intravenously via a peripheral vein over a period of approximately 60 minutes. The IMP will be administered every other week for 52 weeks for a total of 26 doses. No dose modification for GR-MD-02 is allowed. Subjects in the placebo arm will receive placebo diluted in normal saline administered in the same fashion. Active drug and placebo will be blinded (by an unblinded pharmacist) by using amber-colored intravenous bag covers and amber-colored tubing and sealed with tamper-evident tape.

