### **7.9.4 Safety Analyses**

All subjects receiving any part of at least 1 infusion of study treatment will be evaluated for safety. The safety analyses will include evaluation of the incidence of treatment-emergent adverse events (TEAEs), grade 3 or greater AEs, SAEs and AEs leading to discontinuation of study treatment using the Common Terminology Criteria for Adverse Events Version 4.0 or higher. Laboratory and vital sign measurement will be evaluated over time on study using descriptive statistics. Shift analyses of relevant clinical laboratory parameters will be produced showing shifts across low, normal, and high categories.

All heart rate (beats per minute), 12-lead ECG parameters, PR interval (milliseconds), QRS interval (milliseconds), QT interval (milliseconds), and QTc interval (milliseconds) will be measured, and overall interpretation will be summarized for all subjects by study visit including the last visit of the study.

Electrocardiogram parameters will be summarized using descriptive statistics. Mean and mean change from baseline values will be presented for every scheduled assessment. Change from baseline will be calculated as the postbaseline measurement minus the baseline measurement. If either the baseline or postbaseline value is missing, the observation will not be included in the change from baseline summary. In addition, counts and percentages for ECG overall interpretation (normal, abnormal, clinically significant, and not clinically significant) will be presented for each scheduled assessment.

For physical examinations, the results (normal, abnormal, or not done) by body system of the full physical examination at the randomization visit and follow-up visits will be summarized with descriptive statistics by treatment group and visit. For physical examinations performed at postrandomization time points, the number and percentage of subjects with no change or any significant changes since the previous examination will be presented by treatment received. In addition, a shift table will be included to summarize the number and percentage of subjects with changes from baseline to each postrandomization visit by body system for each treatment group. The number and percentage of subjects with normal and abnormal results (clinically significant versus not clinically significant) for each body system will be presented by treatment group.

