9.1. Adverse Events

An adverse event (AE), including serious AE (SAE), is defined as any untoward medical occurrence in a subject enrolled into this study, regardless of its causal relationship to IMP.

A treatment-emergent adverse event (TEAE) is defined as any event which occurs on or after the first double-blind dose date and up to 30 days after the last dose date of the double-blind study drug.

In order to determine a TEAE when the start date of an AE is missing or incomplete, it will be assumed to have occurred after the first infusion of IMP except if an incomplete date indicates that the event started prior to the first infusion.

In the event that only a partial end date (month/year) is available, and the month/year occurs before Day 1 of the study, the AE will not be considered treatment-emergent. However, the partial onset date (month/year) of AE will be handled as follows (where UK, UKN and UKNW indicate unknown or missing Day, Month and Year respectively):

- UK-MMM-YYYY:
 - impute the last day of the month, if the year is less than the first dose year or the year is the same as the first dose year and the month is less than or equal to the first dose month;
 - impute 01-MMM-YYYY, if the year is greater than the first dose year or the year is the same as the first dose year and the month is greater than the first dose month;
 - impute the date of the first dose, if the month and year are the same as the first dose month and year.
- UK-UKN-YYYY:
 - impute 31-DEC-YYYY, if the year is less than the first dose year;

- impute 01-JAN-YYYY, if the year is greater than the first dose year;
- impute the date of the first dose, if the year are the same as the first dose year.
- UK-UKN-UKNW: impute date of the first dose.

If the AE end date is complete and the partial AE start date imputed by the rules above is after the AE end date, then the start date will be imputed by the AE end date.

All AEs will be coded according to the most recent version of the Medical Dictionary for Regulatory Activities (MedDRA), version 18.0. Severity of AE will also be reported according to the NCI Common Terminology Criteria for Adverse Events version 4.03.

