9.1.2. Severity of Adverse Events

All AEs will be summarized by maximum severity (1, 2, 3, 4 and 5). If a subject reports multiple occurrences of a specific event within a specific analysis period, the subject will be counted only once by the maximum severity. No imputation will be done for missing severity.

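### Investigators are told to rate AE severity on three levels, the safety tables need CTCAE grades 1 to 5, and neither document links the two scales

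*Protocol*

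**What the plan says.** **Collection.** Protocol 6.4.5.4 is the only instruction on severity in the AE assessment section: "The intensity of the AE will be rated as mild, moderate, or severe". The levels are defined by interference with daily activities and need for treatment. The top level is open-ended: "Severe events are usually incapacitating". Protocol 6.4.5.3 lists the items recorded for each AE, among them one "investigator-specified assessment of severity and relationship to IMP", and separately seriousness and outcome. No CTCAE grade is listed.

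**Protocol analysis.** Section 7.9.4 plans the incidence of TEAEs and of "grade 3 or greater AEs, SAEs and AEs leading to discontinuation of study treatment using the Common Terminology Criteria for Adverse Events Version 4.0" or a later version. The Safety Assessments part of the synopsis uses the same standard. The Statistical Methods part of the synopsis says instead that TEAEs are graded by the protocol's guidelines, and the only such guideline is the three-level scale.

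**SAP analysis.** SAP 9.1 states: "Severity of AE will also be reported according to the NCI Common Terminology Criteria for Adverse Events version 4.03". Its list of AE summaries includes severity from 1 to 5 and three categories restricted to grade 3 or higher. SAP 9.1.2 begins "All AEs will be summarized by maximum severity (1, 2, 3, 4 and 5", and says missing severity will not be imputed. No summary by mild, moderate and severe is planned.

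**The concern.** The scale that sites are told to use is not the scale that is analysed. Followed literally, 6.4.5.4 yields a rating that no SAP table uses, while the SAP's graded tables have no stated source.

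At stake are the counts by arm of AEs of grade 3 or higher in a three-arm placebo-controlled trial, an analysis named in the synopsis, the protocol body and the SAP. If nobody has fixed who assigns the grade, when, and from what information, different reasonable choices can give different counts. The two scales also differ in kind. Protocol 6.4.5.2 and 6.4.7 require AEs to be recorded from laboratory, ECG and vital sign findings, and a scale based on daily activities says little about a laboratory abnormality without symptoms.

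**Working it through.** The plan gives no figure to reproduce and no power or error-rate calculation applies. The check sets the texts side by side and looks for a bridge between them.

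| Step | Place | Scale |
|---|---|---|
| Instruction to the investigator | Protocol 6.4.5.4 | 3 levels |
| Item recorded per AE | Protocol 6.4.5.3 | one investigator severity assessment |
| Grading of TEAEs | Protocol synopsis, Statistical Methods | the protocol's guidelines, so 3 levels |
| Safety analysis | Protocol synopsis, Safety Assessments; 7.9.4 | CTCAE 4.0 or later, grade 3 or higher |
| Severity reporting | SAP 9.1 | CTCAE 4.03 |
| Severity tables | SAP 9.1, 9.1.2 | grades 1 to 5 |

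1. **Is there a bridge?** Neither document instructs investigators to grade by CTCAE, and neither maps mild, moderate and severe to grades. The protocol names CTCAE only in analysis text.

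2. **Can the rating fill a table with rows 1 to 5?** If each level is given one grade, three levels fill at most three rows, so at least 5 − 3 = 2 rows stay empty whatever happened to the subjects.

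3. **Can the rating give grade 3 or higher?** Only if severe is taken to mean exactly grade 3 and above. Neither document says so.

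4. **How many SAP summaries depend on a grade?** SAP 9.1 lists 15 categories. Four need a grade: severity 1 to 5 of AEs, AEs of grade 3 or higher, TEAEs of grade 3 or higher, and serious TEAEs of grade 3 or higher. The other 15 − 4 = 11 (for example SAEs, relationship to study drug, discontinuation, death) do not. SAP 9.1.2 reads as the detail of the first of the four, so it is not counted again.

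5. **What can be recovered from other fields?** Protocol 6.4.5.3 also collects outcome and seriousness, and the SAE definition in 6.4.5.1 covers death and immediate threat to life. On the assumption that grade 5 means fatal and grade 4 life-threatening (the documents do not print the grade definitions), outcome identifies grade 5. Seriousness identifies grade 4 only if the individual criterion is recorded, which is not stated. Protocol 6.4.5.6 also exempts some events that meet serious criteria from SAE reporting, including expected disease progression, so this route may miss some. No such derivation is specified in either document.

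**The case against.** The best defence is that the information may exist. The word also in SAP 9.1 can be read as a CTCAE grade held alongside the three-level rating. The list in Protocol 6.4.5.3 is introduced as what the record includes, so it need not be exhaustive. Neither the eCRF nor the Study Manual is available. This stands: a reader might infer that grades were never collected, or that the tables would rest on a conversion improvised afterwards, and the documents show neither. What they show is that the instruction and the conversion rule are missing.

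A reader might also infer that grade 4 and grade 5 events go unrecorded. That is too strong, because outcome and seriousness are collected. It is true only of the severity rating itself.

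The SAP may also follow a later protocol than the original of 20 February 2015 supplied here. It restricts entry to Ishak stage 5 or 6, adds Ishak and Brunt-Kleiner staging endpoints, adds nondosing PK visits, and cites MedDRA 18.0 against 17.1. Section 6.4.5.4 could have been amended in between. This weakens the comparison of SAP with protocol but not the conflict within the protocol, where 6.4.5.4 disagrees with 7.9.4 and with the synopsis "TEAEs leading to discontinuation of study treatment using the Common Terminology Criteria for Adverse Events Version 4.0 or higher".

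Finally, the safety endpoints in Protocol 7.4 and SAP 3.2.4 name the incidence of AEs without reference to grade. That is correct, and it limits the reach of the point.

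**Conclusion.** The contradiction is real. The protocol collects severity on one scale and plans to analyse it on another, the SAP builds on the second, and nothing connects them. Four of the 15 AE categories in SAP 9.1 cannot be produced from the 6.4.5.4 rating alone.

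The conclusion rests on the documents as supplied: no eCRF, and possibly a protocol version earlier than the one the SAP was written for. It does not extend to efficacy, to the overall AE and SAE counts, or to the discontinuation and death tables. It would be wrong to read it as showing that all safety analysis fails or that the graded tables could not be filled by any route.

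**What to change.** **Preferred.** Amend Protocol 6.4.5.4 and the AE eCRF page so that the investigator assigns a CTCAE grade from 1 to 5, version 4.03, to every AE. Keep mild, moderate and severe only for terms with no CTCAE entry, with a prespecified map to grades. Align the synopsis statement on grading TEAEs with this.

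**If collection can no longer change.** Have the SAP tabulate mild, moderate and severe as collected. Define grade 3 or higher, before unblinding, by an explicit rule using the severity rating, the seriousness criterion and the outcome.

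**If grades were in fact captured on the eCRF.** State in both documents who assigned them and under which version.

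The first option costs protocol wording, one eCRF field and brief site training. The second costs one derivation rule and one table.
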